pregnancy test weekly for the first 4 weeks and then every 14 days while on therapy (including breaks in therapy), at discontinuation of lenalidomide and at Day 14 and Day 28 post the last dose of lenalidomide (see [Appendix VI](#): Risks of Fetal Exposure, Pregnancy Testing Guidelines and Acceptable Birth Control Methods).

- 2) ≤ 30 days prior to registration
 - 3) Specific testing required only if used to assess disease response
 - 4) Required to document complete response; if response, repeat (mail-in acceptable) to confirm response at ≥ 4 weeks. Bone marrow biopsy does not need confirmation. (Bone marrow biopsy will occur one time as clinically indicated.)
 - 5) Only enough lenalidomide for one cycle of therapy will be supplied to the patient each cycle. After the first 3 months, the drug may be mailed out to the patient if clinical evaluation and blood tests can be obtained per test schedule and mailed/faxed to Mayo Clinic, and patient can return at least every 3 months for follow up to Mayo Clinic. In place of physical exam, RNs will phone patient for adverse event assessment. All unused study drug must be returned to Mayo Clinic and all study drug must be accounted for. CBC and pregnancy testing may be done at local clinic.
 - 6) TSH to be repeated every three months, for patients on active treatment.
 - 7) ± 7 days
 - 8) Lenalidomide must be prescribed through and in compliance with Celgene's Revlimid REMS program. Prescriptions must be filled within 7 days.
 - 9) The patient should be contacted by a nurse 30 days (± 2 days) after the last dose of study treatment (or at the time of initiation of subsequent treatment if started before 30 days) to check if the patient has experienced any late adverse events. Grade 3 or higher adverse events and all serious adverse events (SAEs) at least possibly related to study treatment and deaths due to any cause should be reported as a late adverse event on the event monitoring form if they were not already reported on the nadir/AE form for the last cycle and they occurred prior to any subsequent treatment.
 - 10) CBC should be done weekly during Cycle 1. After Cycle 1, CBC should be done pre-treatment and mid-cycle every cycle. CBC should also be done at the end of treatment. CBC testing may be done at local clinic.
- R Research funded (see [Section 19.0](#)). Will be charged to study and not to patient's account.

5.0 Grouping/Stratification Factors:

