10.0 Adverse Event (AE) Reporting and Monitoring

10.1 Adverse Event Characteristics

CTCAE term (AE description) and grade: The descriptions and grading scales found in the revised NCI Common Terminology Criteria for Adverse Events (CTCAE) version 4.0 will be utilized for AE reporting. All appropriate treatment areas should have access to a copy of the CTCAE version 4.0. A copy of the CTCAE version 4.0 can be downloaded from the CTEP web site:

(http://ctep.cancer.gov/protocolDevelopment/electronic_applications/ctc.htm)

10.11 Adverse event monitoring and reporting is a routine part of every clinical trial. First, identify and grade the severity of the event using the CTCAE version 4.0. Next, determine whether the event is expected or unexpected (see Section 10.2) and if the adverse event is related to the medical treatment or procedure (see Section 10.3). With this information, determine whether the event must be reported as an expedited report (see Section 10.4). **Important:** Expedited adverse event reporting requires submission of a MedWatch 3500A report(s). Expedited reports are to be completed within the timeframes and via the mechanisms specified in Sections 10.4. All AEs reported via expedited mechanisms must also be reported via the routine data reporting mechanisms defined by the protocol (see Sections 10.52 and 18.0).

10.12 Each CTCAE term in the current version is a unique representation of a specific event used for medical documentation and scientific analysis and is a single MedDRA Lowest Level Term (LLT). Grade is an essential element of the Guidelines and, in general, relates to **severity** for the purposes of regulatory reporting to NCI.

NOTE: A severe AE, as defined by the above grading scale, is **NOT** the same as serious AE which is defined in the table in Section 10.4.

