10.3 Assessment of Attribution

When assessing whether an adverse event is related to a medical treatment or procedure, the following attribution categories are utilized:

Definite - The adverse event *is clearly related* to the agent(s).

Probable - The adverse event *is likely related* to the agent(s).

Possible - The adverse event *may be related* to the agent(s).

Unlikely - The adverse event *is doubtfully related* to the agent(s).

Unrelated - The adverse event *is clearly NOT related* to the agent(s).

Events determined to be possibly, probably or definitely attributed to a medical treatment suggest there is evidence to indicate a causal relationship between the drug and the adverse event.

10.4 Expedited Reporting Requirements for Studies using Commercial Agent(s) ONLY:

Expedited Reporting Requirements for Adverse Events that Occur in a Non-IND/IDE trial within 30 Days of the Last Administration of a Commercial Imaging Agent^{1,2}

FDA REPORTING REQUIREMENTS FOR SERIOUS ADVERSE EVENTS (21 CFR Part 312) NOTE: Investigators MUST immediately report to the sponsor ANY Serious Adverse Events, whether or not they are considered related to the investigational agent(s)/intervention (21 CFR 312.64) An adverse event is considered serious if it results in ANY of the following outcomes:
 
 1) Death 2) A life-threatening adverse event 3) An adverse event that results in inpatient hospitalization or prolongation of existing hospitalization for ≥ 24 hours 4) A persistent or significant incapacity or substantial disruption of the ability to conduct normal life functions 5) A congenital anomaly/birth defect. 6) Important Medical Events (IME) that may not result in death, be life threatening, or require hospitalization may be considered serious when, based upon medical judgment, they may jeopardize the patient or subject and may require medical or surgical intervention to prevent one of the outcomes listed in this definition. (FDA, 21 CFR 312.32; ICH E2A and ICH E6). 				

ALL SERIOUS adverse events that meet the above criteria MUST be immediately reported to the sponsor within the timeframes detailed in the table below.
				
Hospitalization	Grade 1 Timeframes	Grade 2 Timeframes	Grade 3 Timeframes	Grade 4 & 5 Timeframes
Resulting in Hospitalization ≥24 hrs	7 Calendar Days			24-Hour 3 Calendar Days
Not resulting in Hospitalization ≥ 24 hrs	Not required		7 Calendar Days	

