
NOTE Protocol specific exceptions to expedited reporting of serious adverse events are found in section 10.41 of the protocol.
 
Expedited AE reporting timelines are defined as:
 
 ○ “24-Hour; 3 Calendar Days” - The AE must initially be reported via MedWatch within 24 hours of learning of the AE, followed by a complete expedited report within 3 calendar days of the initial 24-hour report. ○ “7 Calendar Days” - A complete expedited report on the AE must be submitted within 7 calendar days of learning of the AE. 				

¹Serious adverse events that occur more than 30 days after the last administration of investigational agent/intervention and have an attribution of possible, probable, or definite require reporting as follows: Expedited 24-hour notification followed by complete report within 3 calendar days for:
 
 • All Grade 4, and Grade 5 AEs 
Expedited 7 calendar day reports for:
 
 • Grade 2 adverse events resulting in hospitalization or prolongation of hospitalization • Grade 3 adverse events 
² For studies using PET or SPECT IND agents, the AE reporting period is limited to 10 radioactive half-lives, rounded UP to the nearest whole day, after the agent/intervention was last administered. Footnote “1” above applies after this reporting period.
 
Effective Date: May 5, 2011
				

Additional Instructions:

1. An increased incidence of an expected adverse event (AE) is based on the patients treated for this study at their site. A list of known/expected AEs is reported in the package insert or the literature, including AEs resulting from a drug overdose.
2. Submit form 3500A to the FDA, MedWatch, [REDACTED]

Mayo Clinic Cancer Center (MCCC) Institutions: Use MCCC SAE Reporting Form

[REDACTED]
 Provide copies of MedWatch and SOBI SAE forms to the MCCC Regulatory Affairs Unit (RAU) Risk Information Specialist [REDACTED] who will determine and complete IRB reporting. The RAU will submit to the MCCC SAE Coordinator.

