10.6 Required Routine Reporting

Adverse events to be graded at each evaluation and pretreatment symptoms/conditions to be evaluated at baseline per the CTCAE v4.0 grading unless otherwise stated in the table below:

SYSTEM ORGAN CLASS	Adverse event/Symptoms	Baseline	Each evaluation
Investigations	Creatinine increased	X	X
	Neutrophil count decreased	X	X
	Platelet count decreased	X	X
	Lymphocyte count decreased	X	X
	White blood cell decreased	X	X
	Anemia	X	X
General disorders and administration site conditions	Fatigue	X	X
	Injection site reaction		X
Gastrointestinal Disorders	Nausea	X	X
	Vomiting	X	X
	Diarrhea		X
	Constipation		X
	Number of stools	X	
Renal and urinary disorders	Chronic kidney disease (decreased creatinine clearance)	X	X
Skin and subcutaneous tissue disorders	Rash, maculopapular	X	X
Nervous system disorders	Peripheral sensory neuropathy	X	X
Constitutional Symptoms	Insomnia	X	X
Vascular Disorders	Thromboembolic event	X	X

10.61 Submit via appropriate MCCC Case Report Forms (i.e., paper or electronic, as applicable) the following AEs experienced by a patient and not specified in Section 10.6 (above):

10.611 Grade 2 AEs deemed *possibly, probably, or definitely* related to the study treatment or procedure.

10.612 Grade 3 and 4 AEs regardless of attribution to the study treatment or procedure.

10.613 Grade 5 AEs (Deaths)

10.6131 Any death within 30 days of the patient's last study treatment or procedure regardless of attribution to the study treatment or procedure.

- 10.6132 Any death more than 30 days after the patient's last study treatment or procedure that is felt to be at least possibly treatment related must also be submitted as a Grade 5 AE, with a CTCAE type and attribution assigned.
- 10.62 Refer to the instructions in the Forms Packet (or electronic data entry screens, as applicable) regarding the submission of late occurring AEs following completion of the Active Monitoring Phase (i.e., compliance with Test Schedule in [Section 4.0](#)).
- 10.7 All serious adverse events (SAEs) will be followed until resolution or death.

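### Footnote 9 of the Test Schedule conflicts with Section 10 on which events within 30 days of the last dose are recorded, so late all-cause adverse events may be incomplete in the phase II tables

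*Combined protocol and SAP*

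**What the plan says.** Section 4.0, footnote 9, schedules a nurse contact 30 days (plus or minus 2) after the last dose, or at the start of subsequent treatment if that comes sooner. The items for the event monitoring form are "Grade 3 or higher adverse events and all serious adverse events (SAEs) at least possibly related to study treatment", together with deaths from any cause. Two conditions apply to the whole list: the event is not already on the last cycle's nadir/AE form, and it happened before any subsequent treatment.

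Section 10 sets these rules:

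- **10.4** requires investigators to report "ANY Serious Adverse Events, whether or not they are considered related to the investigational agent(s)/intervention". Its table covers the 30 days after last administration. Footnote 1 to that table applies an attribution condition only to serious "adverse events that occur more than 30 days after the last administration of investigational agent/intervention and have an attribution of possible, probable, or definite".
- **10.11**: "All AEs reported via expedited mechanisms must also be reported via the routine data reporting mechanisms defined by the protocol".
- **10.612** asks for "Grade 3 and 4 AEs regardless of attribution to the study treatment or procedure", with no post-treatment window stated.
- **10.6131** asks for "Any death within 30 days of the patient's last study treatment or procedure regardless of attribution", and 10.52 requires expedited reporting of deaths in the same window.
- **10.62** refers late events after Active Monitoring to the Forms Packet, which is not among the documents.

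None of these rules makes an exception once new therapy has started.

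**The concern.** The two sections give site staff different instructions for the same 30 days. Footnote 9 uses attribution as an entry condition inside a window where Section 10.4 does not. It also closes the window early for any patient who starts new therapy before day 30.

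Objective 2.22 compares toxicity between the arms. The phase II analysis in Section 16.34 tabulates the maximum grade of each type of adverse event per patient, and relationship to treatment is an additional consideration, not an entry condition. Those tables need all-cause data. Section 16.362 also promises a review of Grade 4 and 5 events judged unrelated or unlikely to be related, to verify the attribution and detect new treatment-related events. An event left out because it was called unrelated cannot be reviewed from the trial data.

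SAEs must also go to both companies (10.42, 10.43) whatever the form says. If staff follow the footnote, the safety reports and the trial database may not agree.

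**Working it through.** No arithmetic applies, because the documents give no late-event rates. The check is to apply both sets of rules to each kind of event.

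The relatedness qualifier in footnote 9 can be read in two ways. On the narrow reading it modifies SAEs only. On the broad reading it also modifies Grade 3 or higher events. The later phrase on deaths from any cause makes the broad reading plausible, but the grammar does not decide it. All rows concern events within 30 days of the last dose that are not already on the last cycle's form.

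| Event | Section 10 | Footnote 9, narrow | Footnote 9, broad |
|---|---|---|---|
| Unrelated Grade 1-2 SAE (e.g. hospitalization of 24 hours or more), before new therapy | Required (10.4, 10.11) | Not recorded | Not recorded |
| Unrelated non-fatal Grade 3-4 SAE, before new therapy | Required (10.4, 10.11) | Recorded, as Grade 3+ | Not recorded |
| Unrelated non-serious Grade 3-4 event, before new therapy | Probably required (10.612; no window stated) | Recorded | Not recorded |
| Related SAE or related Grade 3+ event, before new therapy | SAE required; non-serious probably | Recorded | Recorded |
| Death from any cause, before new therapy | Required (10.52, 10.6131) | Recorded | Recorded |
| SAE, related or not, after new therapy starts | Required (10.4, 10.11) | Not recorded | Not recorded |
| Death after new therapy starts | Required (10.52, 10.6131) | Not recorded as a late event | Not recorded as a late event |

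From the table:

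1. **Attribution and SAEs.** There is a conflict on either reading. Its extent varies from unrelated Grade 1-2 SAEs (narrow) to all unrelated non-fatal SAEs (broad).
2. **New-therapy cut-off.** There is a conflict on either reading, and it reaches related events and deaths. For example, if new therapy starts on day 14, a related SAE or a death on day 20 is required by Section 10 and excluded by footnote 9.
3. **Non-serious Grade 3-4 events.** The attribution conflict arises only on the broad reading. Even then it is likely but not firm, because 10.612 names no window and 10.62 defers to the Forms Packet.
4. **Deaths.** They are exempt from the attribution limit. Only the cut-off affects them.

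Scope: notes in Sections 13.0 and 18.0 state that phase I event monitoring is no longer required as of Addendum 5. The point therefore concerns phase II.

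**The case against.** The strongest reply is that footnote 9 is only a residual net. The test schedule has an end-of-treatment assessment, and Section 18.12 makes the Nadir/Adverse Event form due then, where 10.612 applies regardless of attribution. Toxicity that led to stopping would normally be on that form. Section 10 also stays in force: SAEs still go by expedited report, 10.11 still sends them to the routine data, and the event monitoring form in 18.13 has its own entry for death. Because 16.34 uses the maximum grade per event type, a missed event changes a patient's entry only if it exceeds the grade already recorded. Ending capture at new therapy also keeps the next regimen's toxicity out of the comparison.

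Much of this stands, and it limits the harm. It does not remove the conflict: if Section 10 still applies, staff hold two incompatible instructions for one contact. A start-date flag separates the next regimen's toxicity without discarding Section 10 events.

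A reader might infer more than the documents support:

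- **That toxicity is under-counted.** Section 16.232 (phase I plan) defines toxicity as related events, and the 16.362 stopping rule counts only related events. The attribution limit takes nothing from either; only the cut-off can lose related events.
- **That toxicity peaks after the last dose, or that a given number of events is lost.** The documents contain no rates for this window and no figures on how often events are called unrelated.
- **That the arm comparison is biased.** Attribution or the time to new therapy could differ by arm, but phase II is planned as double-blind and nothing in the documents shows a difference.

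**Conclusion.** The conflict is real and worth correcting before phase II data are collected under it. Two parts hold on any reading: an attribution limit on SAEs inside 30 days, and a stop at new therapy that covers deaths and related events. The consequence is possible incompleteness of late all-cause events in the 16.34 tables and in the 16.362 review of Grade 4-5 events judged unrelated, and possible absence of some related events from the late record. It is not a loss of SAEs to the sponsor, who should still receive them by expedited report.

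The size of the gap cannot be derived from the documents. It depends on which reading staff adopt, how many patients start new therapy within 30 days, and what the Forms Packet says. The conclusion assumes that the Forms Packet does not already override footnote 9.

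**What to change.** Rewrite footnote 9 to match Section 10:

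- At the 30-day contact, record on the case report form all SAEs and all deaths within 30 days of the last dose, regardless of attribution.
- State that Grade 3 or higher events are recorded on the same basis as in 10.612, which removes the ambiguity about what the relatedness qualifier covers.
- Make the contact at day 30 even if new therapy has started. Record the start date of that therapy as a flag, so that tables can be shown with and without later events.
- Apply the attribution limit only after 30 days, as in footnote 1 of the 10.4 table.
- Reconcile the text with 10.61, 10.62 and the Forms Packet.

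The cost is one footnote and one form instruction; the nurse contact is already scheduled. The downside is a few more events to enter. Some will be due to the next therapy, but events after its start can be identified from the flag.

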5.1 Grouping Factors

5.11 Phase: I vs. II

5.2 Stratification Factors (Phase II Only)

5.21 Diagnosis of Active Myeloma: Yes vs. No

5.22 Presence of Myeloma Bone Lesions: Yes vs. No

5.23 Disease Stage (ISS Staging System) > 1 : Yes vs. No

6.0 Registration Procedures

6.1 Phase I Registration Procedures

Prior to discussing protocol entry with the patient, call the MCCC Registration Office [REDACTED] for dose level and to insure that a place on the protocol is open to the patient.

To register a patient, [contact]) a completed eligibility checklist to the Mayo Clinic Cancer Center (MCCC) Registration Office between 8 a.m. and 4:30 p.m. central time Monday through Friday.

6.2 Phase II Registration Procedures

6.21 To register a patient, access the Mayo Clinic Cancer Center (MCCC) web page and enter the registration/randomization application. The registration/randomization application is available 24 hours a day, 7 days a week. Back up and/or system support contact information is available on the Web site. If unable to access the Web site, call the MCCC Registration Office at [contact] between the hours of 8 a.m. and 4:30 p.m. Central Time (Monday through Friday).

The instructions for the registration/randomization application are available on the MCCC web page [REDACTED] and detail the process for completing and confirming patient registration. Prior to initiation of protocol treatment, this process must be completed in its entirety and a MCCC subject ID number must be available as noted in the instructions. It is the responsibility of the individual registering the patient to confirm the process has been successfully completed prior to release of the study agent. Patient registration via the registration/randomization application can be confirmed in any of the following ways:

- Contact the MCCC Registration Office [REDACTED]. If the patient was fully registered, the MCCC Registration Office staff can access the information from the centralized database and confirm the registration.
- Refer to “Instructions for Remote Registration” in section “Finding/Displaying Information about A Registered Subject.”

6.22 Documentation of IRB approval must be on file in the Registration Office before an investigator may register any patients.

In addition to submitting initial IRB approval documents, ongoing IRB approval documentation must be on file (no less than annually) at the Registration Office [REDACTED]. If the necessary documentation is not submitted in advance of attempting patient registration, the registration will not be accepted and the patient may not be enrolled in the protocol until the situation is resolved.

When the study has been permanently closed to patient enrollment, submission of annual IRB approvals to the Registration Office is no longer necessary.

6.3 Phase I and II

6.31 Prior to accepting the registration, the registration/randomization application will verify the following:

- IRB approval at the registering institution
- Patient eligibility
- Existence of a signed consent form

- Existence of a signed authorization for use and disclosure of protected health information
- 6.32 Treatment on this protocol must commence at Mayo Clinic Rochester under supervision of a hematologist
- 6.33 Treatment cannot begin prior to registration.
- 6.34 Pretreatment tests/procedures (see [Section 4.0](#)) must be completed within the guidelines specified on the test schedule.
- 6.35 All required baseline symptoms (see [Section 10.6](#)) must be documented and graded.
- 6.36 Study drug is available on site
- 6.4 Phase II Randomization Procedures
- 6.41 The factors defined in Section 5.0, together with the registering membership, will be used as stratification factors.
- 6.42 After the patient has been registered into the study, the values of the stratification factors will be recorded, and the patient will be assigned to one of the following treatment groups using the Pocock and Simon dynamic allocation procedure which balances the marginal distributions of the stratification factors between the treatment groups
- Len/Dex + Placebo
 - Len/Dex +Anakinra
- 6.5 Procedures for Double-Blinding the Treatment Assignment
- 6.51 After the treatment assignment has been ascertained by the registration/randomization application, the patient's study medication code number will be displayed on the confirmation of registration screen
- 6.52 The data manager/nurse/pharmacist at the patient's institution must contact the MCCC Registration Office for a code number when additional study product is needed for the patient.
- 6.53 The number of the syringe will be recorded on the dosing form.
- 6.54 MCCC Registration Office personnel will monitor the supply of coded bottles at each participating institution

